NCT03550378

A Phase 2a, Randomised, Double-Blind, Placebo-Controlled Study to Evaluate the Efficacy, Safety, and Pharmacokinetics of MEDI0382 in Subjects with Type 2 Diabetes Mellitus and Renal Impairment

Sponsor Protocol Number: D5670C00013

Application Number: EudraCT number 2018-000019-26

Investigational Product: MEDI0382

Sponsor: MedImmune Limited, a wholly owned subsidiary of
AstraZeneca, [name]

Medical Monitor:

[REDACTED]
[REDACTED] MedImmune
Phone: [REDACTED]; Fax: [REDACTED]

Contract Research Organization: Covance, Inc.

Protocol History, Date: Original Protocol, 07Feb2018
Protocol Amendment 1, 28Feb2018
Protocol Amendment 2, 06Apr2018
Protocol Amendment 3, 11Oct2018
Protocol Amendment 4, 12Nov2018

This document contains trade secrets and commercial information that is privileged or confidential and may not be disclosed without prior authorisation from MedImmune.

PROTOCOL SYNOPSIS

TITLE	
A Phase 2a, Randomised, Double-Blind, Placebo-Controlled Study to Evaluate the Efficacy, Safety, and Pharmacokinetics of MEDI0382 in Subjects with Type 2 Diabetes Mellitus and Renal Impairment	
HYPOTHESES	
Primary Hypothesis:	
Administration of MEDI0382 once daily titrated up to a dose level of [REDACTED] will result in superior blood glucose control versus placebo after 32 days of treatment in subjects with type 2 diabetes mellitus (T2DM) and renal impairment.	
Secondary Hypotheses:	

 Administration of MEDI0382 once daily titrated up to a dose level of [REDACTED] across 32 days will be well tolerated in subjects with T2DM and renal impairment Administration of MEDI0382 once daily titrated up to a dose level of [REDACTED] will result in superior weight loss versus placebo after 32 days of treatment in subjects with T2DM and renal impairment Administration of MEDI0382 once daily titrated up to a dose level of [REDACTED] will have a predictable pharmacokinetic (PK) profile in subjects with T2DM and renal impairment 	
OBJECTIVES AND ENDPOINTS	
Objectives	Endpoints
Primary	
To assess the effect of MEDI0382 titrated up to a dose level of [REDACTED] on glucose control versus placebo after 32 days of treatment	
 Percentage change in glucose area under the curve (AUC) as measured by a standardised mixed-meal tolerance test (MMTT) from baseline (Day -5) to the end of 32 days of treatment (Day 32)
Secondary	
To characterise the safety profile and tolerability of MEDI0382 titrated up to a dose level of [REDACTED] during dosing and follow-up in subjects with T2DM and renal impairment	
 Measures of safety and tolerability (adverse events/serious adverse events [AEs/SAEs], vital signs, postural blood pressure [BP] changes, electrocardiogram [ECG], laboratory test results) Change in mean 24-hour pulse rate, systolic and diastolic blood pressure from baseline (Day -5) to the end of dosing at each dose level (Days 4, 11, 18 and 32)
To assess the effects of MEDI0382 titrated up to a dose level of [REDACTED] on additional measures of glycaemic control versus placebo after 32 days of treatment	
 Change in haemoglobin A1c (HbA1c) from baseline (Day 1) to the end of 32 days of treatment (Day 32) Change in fasting glucose from baseline (Day 1) to the end of 32 days of treatment (Day 32) Change in percentage of time spent within a target glucose range of 70 mg/dL (3.9 mmol/L) to 180 mg/dL (10 mmol/L) over a 7-day period at baseline (Days -8 to -2) to the final week of treatment (Days 26-32)
To assess the effects of MEDI0382 titrated up to a dose level of [REDACTED] on weight versus placebo after 32 days of treatment	
 Percentage and absolute change in body weight from baseline (Day 1) to the end of 32 days of treatment (Day 33)

To characterise the PK profile and immunogenicity of MEDI0382	
• PK endpoints: AUC over a dosing duration, maximum observed concentration (C_{max}), time to C_{max} (T_{max}), trough plasma concentration (C_{trough})• Development of anti-drug antibodies (ADA) and titre (if confirmed positive)
Exploratory	
	
	
	

STUDY DESIGN

This is a randomised, double-blind, placebo-controlled study to evaluate the safety, tolerability, efficacy, and PK profile of MEDI0382 titrated from [REDACTED] up to [REDACTED] and administered once daily by subcutaneous (SC) injection over 32 days in subjects with T2DM and renal impairment (eGFR ≥ 30 and < 60 mL/min/1.73 m²). The study has a 14-day run-in period of diet and exercise and continuous glucose monitoring (CGM), a 32-day treatment period, and a 28-day follow-up period. Diet and exercise guidance will be according to local practices. It is planned to randomise approximately 40 subjects across multiple study sites. Subjects will be consented, screened for suitability, and randomised within 40 days of screening, if eligible.

Throughout the study, subjects will have the choice to either travel to the clinic for visits or stay overnight locally whenever consecutive daily visits are required. Subjects will be expected to fast for at least 8 hours overnight prior to Visit 3 (Day -5), Visit 4 (Day 1), Visit 9 (Day 32), and Visit 12 (Day 60).

On Visit 2 (Day -14) subjects will attend the clinical unit for a short visit. At this visit they will be given advice on diet and exercise (in accordance with local practices) and training in SC injection administration, and fitted with a CGM sensor that the subject will be expected to wear continuously for the duration of the study until the second follow-up visit (Visit 11).

On Visit 3 (Day -5), subjects will attend the clinical unit for a long visit and will undergo safety assessments and a mixed-meal tolerance test (MMTT). At this time, an ambulatory blood pressure monitoring (ABPM) device will be fitted on the contralateral arm to the CGM sensor and will be worn for 24 hours.

Subjects will be randomised on Visit 4 (Day 1) to receive either MEDI0382 or placebo and dosing will commence following predose baseline vital signs, blood tests (including HbA1c), an ECG, body weight measurement, [REDACTED]. Subjects will then return for daily dosing or remain overnight locally until Day 5, and thereafter will have visits at weekly intervals until a maintenance dose of [REDACTED] is established. At Visits 6, 7, and 8, ABPM recordings [REDACTED] will be performed. On the last day of dosing (Visit 9; Day 32), subjects will attend for a long day visit and undergo a repeat MMTT, HbA1c, ABPM, [REDACTED] and serial PK sampling alongside safety assessments. On the following day (first follow-up visit, Visit 10; Day 33) subjects will return to the clinic for a blood draw, urine collection, weight measurement, [REDACTED]. Two additional follow-up visits (Visit 11; Day 40 \pm 5 and Visit 12; Day 60 \pm 5) will be performed after the last dose for safety assessments.

TARGET SUBJECT POPULATION

Male and female subjects ≥ 18 and < 85 years of age with renal impairment (eGFR ≥ 30 and < 60 mL/min/1.73 m²) and T2DM, and who may be on insulin and/or combination oral therapies.

TREATMENT GROUPS AND REGIMENS MEDI0382 or placebo will be administered once daily in the morning via SC injection:

- MEDI0382 [REDACTED] once daily for 4 days, followed by [REDACTED] daily for 7 days, [REDACTED] daily for 7 days, and [REDACTED] daily for 14 days (n = 20)
- Placebo once daily for 32 days (n = 20)

STATISTICAL METHODS

Sample size: Forty subjects (20 completers in the MEDI0382 group and 20 completers in placebo group) will provide > 85% power to detect 18.1% difference between the two treatment groups in percentage change in the MMTT glucose AUC from baseline (Day -5) to the end of 32 days of treatment (Day 32), with a two-sided significance level of 0.1 and assuming the standard deviation of 20%.

Statistical analyses: The primary efficacy analysis will be performed using the intent-to-treat (ITT) population. The primary efficacy endpoint, percentage change in MMTT glucose AUC from baseline (Day -5) to the end of 32 days of treatment will be analysed using an analysis of covariance (ANCOVA) model. The model will include fixed effect of treatment and baseline AUC as a covariate. The difference of the percent change in glucose AUC between the two treatment arms will be compared with a two-sided significance level of 0.10. Secondary efficacy analyses will be performed using the ITT population. All secondary efficacy endpoints will be summarised by visit and by treatment group. The change in percentage of time spent within a target glucose range of 70 mg/dL (3.9 mmol/L) to 180 mg/dL (10 mmol/L) over a 7-day period at baseline to the final week of treatment will be analysed using a Wilcoxon rank-sum test. All other continuous endpoints will be analysed using a similar ANCOVA model as that for the primary analysis.

Safety analyses will be performed using the as-treated population. AEs and SAEs will be coded by the most updated version of Medical Dictionary for Regulatory Activities (MedDRA), and the type, incidence, severity, and relationship to study investigational product will be summarised by MedDRA System Organ Class and Preferred Term and by treatment. AEs leading to discontinuation, AEs leading to death, and deaths will also be summarised. Specific AEs will be counted once for each subject for calculating percentages. In addition, if the same AE occurs multiple times within a particular subject, the highest severity and level of relationship observed will be reported. Subject-level data listings of all AEs will be presented. Other safety data, such as vital signs, clinical laboratory data, ECG, and physical examination findings will be descriptively summarised at each time point by treatment. Mean ambulatory blood pressure and pulse rate measurements recorded over 24 hours at different time-points will be analysed using an ANCOVA model, adjusting for treatment and measurement at baseline.

Pharmacokinetic analyses: Pharmacokinetic parameters such as maximum concentration (C_{max}), time to maximum observed concentration (T_{max}), and AUC_{tau} , will be estimated from plasma concentration-time data for MEDI0382 at the [REDACTED] dose level. Descriptive statistics will be generated for PK parameters for the MEDI0382 group at [REDACTED] and for C_{trough} at each dose level.

Immunogenicity analyses: The incidence and impact of ADA to MEDI0382 will be evaluated. The number and percentage of subjects with confirmed positive serum antibodies to MEDI0382 will be reported by treatment.

Interim analysis: No interim analysis is planned for this study.

TABLE OF CONTENTS

PROTOCOL SYNOPSIS	2
TABLE OF CONTENTS	6
LIST OF ABBREVIATIONS	11
1 INTRODUCTION	13
1.1 Disease Background	13
1.2 MEDI0382 Background.....	13
█	█
█	█
█	█
1.6 Benefit-risk and Ethical Assessment	15
1.7 Research Hypotheses	15
1.7.1 Primary Hypothesis	15
1.7.2 Secondary Hypotheses.....	15
2 OBJECTIVES AND ENDPOINTS.....	16
2.1 Primary Objective and Associated Endpoint	16
2.2 Secondary Objectives and Associated Endpoints.....	16
█	█
3 STUDY DESIGN	20
3.1 Description of the Study	20
3.1.1 Overview	20
3.1.2 Treatment Regimen.....	21
3.1.3 Dose Escalation	22
█	█
3.2 Rationale for Dose, Population, and Endpoints	26
3.2.1 Dose Rationale.....	26
3.2.2 Rationale for Study Population	28
3.2.3 Rationale for Endpoints	28
4 MATERIALS AND METHODS	30
4.1 Subjects	30
4.1.1 Number of Subjects	30
4.1.2 Inclusion Criteria	30
4.1.3 Exclusion Criteria	31
4.1.4 Subject Enrollment and Randomisation.....	33
4.1.5 Withdrawal from the Study.....	33
4.1.6 Discontinuation of Investigational Product.....	34
4.1.7 Replacement of Subjects.....	34
4.1.8 Withdrawal of Informed Consent for Data and Biological Samples.....	35
4.2 Schedule of Study Procedures.....	36
4.2.1 Enrollment/Screening Period	36

4.2.2	Randomised Treatment Period	39
4.2.3	Follow-up Period	45
4.3	Description of Study Procedures	46
4.3.1	Efficacy	46
4.3.1.1	Mixed-meal Tolerance Tests	46
4.3.1.2	Blood Tests for Glucose Lowering Efficacy	47
4.3.1.3	Weight	47
4.3.2	Medical History, Physical Examination, Electrocardiogram, Weight, and Vital Signs	47
4.3.2.1	Medical History and Physical Examination	47
4.3.2.2	Electrocardiograms	48
4.3.2.3	Assessment of the Injection Site	48
4.3.2.4	Vital Signs	48
4.3.3	Clinical Laboratory Tests	49
4.3.4	Pharmacokinetic Evaluation and Methods	50
4.3.5	Immunogenicity Evaluation and Methods	50

RBC	red blood cell
SAE	serious adverse event
SAP	statistical analysis plan
SC	subcutaneous
SGLT2	sodium-glucose co-transporter 2
SID	subject identification
SOC	system organ class
T2DM	type 2 diabetes mellitus
TEAE	treatment emergent adverse event
T _{max}	time to maximum concentration
ULN	upper limit of normal
WBC	white blood cell
w/v	weight per volume

1 INTRODUCTION

1.1 Disease Background

The rising prevalence of type 2 diabetes mellitus (T2DM) and obesity is a cause of substantial health and economic burden worldwide. In many cases of T2DM, significant weight loss (typically 5% of body weight or more) can promote improvements in glycaemic control, cardiovascular risk, and mortality rates, and may even slow or reverse disease progression (Petersen et al, 2005). Many existing therapies for T2DM focus upon lowering blood glucose; however, there is a major unmet need for treatments that both improve glycaemic control and achieve disease-modifying weight loss.

Renal impairment attributed to chronic hyperglycaemia and hypertension is common in patients with longstanding T2DM, and is often exacerbated by obesity. Patients with significant renal impairment and T2DM therefore stand to benefit from medications that can deliver both improvements in glycaemic control and weight loss.

1.2 MEDI0382 Background

MEDI0382 is briefly described below. Refer to the current Investigator's Brochure (IB) for details.

MEDI0382 is a synthetic peptide with both glucagon-like peptide-1 (GLP-1) and glucagon receptor co-agonist activity, which is under development for the treatment of T2DM and obesity. GLP-1 receptor agonists are established treatments for T2DM that improve glycaemic control, delay gastric emptying, and depress appetite leading to modest, but often non-sustained weight loss (typically 3% versus baseline at one year). Glucagon has similar effects to GLP-1 on gastric emptying and appetite, and has also been shown to promote increased energy expenditure (Lynch et al, 2014; Habegger et al, 2013). Oxyntomodulin, a naturally occurring peptide with GLP-1 and glucagon receptor co-agonist activity, has been shown to promote weight loss through effects on appetite and energy expenditure (Wynne et al, 2006) and co-infusion of GLP-1 and glucagon has synergistic effects on reducing food intake and promoting weight loss in human subjects (Bagger et al, 2015).

1.3 Summary of Nonclinical Experience

[REDACTED]

1.4 Summary of Clinical Experience

[REDACTED]

[REDACTED]

Refer to the current MEDI0382 IB for a complete summary of clinical information.

1.5 Rationale for Conducting the Study

[REDACTED]

1.6 Benefit-risk and Ethical Assessment

The study will be performed in accordance with ethical principles that have their origin in the Declaration of Helsinki and are consistent with ICH/GCP, and applicable regulatory requirements.

MEDI0382 is a synthetic peptide with both GLP-1 and glucagon receptor co-agonist activity that promote glucose lowering and weight loss and is targeted at subjects with T2DM. MEDI0382 has the potential to deliver improvements in glycaemic control and lipid homeostasis, and is predicted to be a useful therapy for T2DM.

The study design aims to minimise potential risks to subjects participating in this study based on the proposed inclusion/exclusion criteria, safety monitoring, and up-titration dosing schedule. All subjects will be monitored throughout the study to ensure adequate glycaemic control. Subjects will be given appropriate training in subcutaneous (SC) injection administration as well as use of any devices.

Refer to the current IB for information on the potential benefits of MEDI0382 and an assessment of the potential and known risks.

1.7 Research Hypotheses

1.7.1 Primary Hypothesis

- Administration of MEDI0382 once daily titrated up to a dose level of [REDACTED] will result in superior blood glucose control versus placebo after 32 days of treatment in subjects with T2DM and renal impairment.

1.7.2 Secondary Hypotheses

- Administration of MEDI0382 once daily titrated up to a dose level of [REDACTED] across 32 days will be well tolerated in subjects with T2DM and renal impairment
- Administration of MEDI0382 once daily titrated up to a dose level of [REDACTED] will result in superior weight loss versus placebo after 32 days of treatment in subjects with T2DM and renal impairment
- Administration of MEDI0382 once daily titrated up to a dose level of [REDACTED] will have a predictable pharmacokinetic (PK) profile in subjects with T2DM and renal impairment

2 OBJECTIVES AND ENDPOINTS

2.1 Primary Objective and Associated Endpoint

Table 1 Primary Objective and Associated Endpoint

Type	Objective	Endpoint
Efficacy	To assess the effect of MEDI0382 titrated up to a dose level of [REDACTED] on glucose control versus placebo after 32 days of treatment	
 Percentage change in glucose area under the curve (AUC) as measured by a standardised mixed-meal tolerance test (MMTT) from baseline (Day -5) to the end of 32 days of treatment (Day 32)

2.2 Secondary Objectives and Associated Endpoints

Table 2 Secondary Objectives and Associated Endpoints

Type	Objective	Endpoints
Safety	To characterise the safety profile and tolerability of MEDI0382 titrated up to a dose level of [REDACTED] during dosing and follow-up in subjects with T2DM and renal impairment	
 Measures of safety and tolerability (adverse events/serious adverse events [AEs/SAEs], vital signs, postural blood pressure [BP] changes, electrocardiogram [ECG], laboratory test results) Change in mean 24-hour pulse rate, systolic and diastolic blood pressure from baseline (Day -5) to the end of dosing at each dose level (Days 4, 11, 18, and 32)
Efficacy	To assess the effects of MEDI0382 titrated up to a dose level of [REDACTED] on additional measures of glycaemic control versus placebo after 32 days of treatment	
 Change in haemoglobin A1c (HbA1c) from baseline (Day 1) to the end of 32 days of treatment (Day 32) Change in fasting glucose from baseline (Day 1) to the end of 32 days of treatment (Day 32) Change in percentage of time spent within a target glucose range of 70 mg/dL (3.9 mmol/L) to 180 mg/dL (10 mmol/L) over a 7-day period at baseline (Days -8 to -2) to the final week of treatment (Days 26-32)
Efficacy	To assess the effects of MEDI0382 titrated up to a dose level of [REDACTED] on weight versus placebo after 32 days of treatment	
 Percentage and absolute change in body weight from baseline (Day 1) to the end of 32 days of treatment (Day 33)

Table 2 Secondary Objectives and Associated Endpoints

Type	Objective	Endpoints
PK/Immunogenicity	To characterise the PK profile and immunogenicity of MEDI0382	
• PK endpoints: AUC over a dosing duration, maximum observed concentration (C_{max}), time to C_{max} (T_{max}), trough plasma concentration (C_{trough})• Development of anti-drug antibodies (ADA) and titre (if confirmed positive)

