4.2.2 Randomised Treatment Period

Table 10 shows all procedures to be conducted during the treatment period.

Table 10 Treatment Period Study Procedures

Visit Number	V4 ^a	V5	V6	V7	V8	V9 ^a
Procedure / Study Day	D1	D2, D3, D4	D5	D12	D19	D32
Daily visits for dosing ^b		X				
Outpatient visit to clinic ^c	X		X	X	X	X
Concomitant medications	X	X	X	X	X	X
Physical examination (abbreviated)	X		X	X	X	X
Vital signs ^d	X		X	X	X	X
ABPM ^e			X	X	X	X
ECG ^f	X		X	X	X	X
Body weight ^g	X		X	X	X	X
	■		■	■	■	■
Randomisation	X					
IP administrationⁱ (SC)	X	X	X	X	X	X
Dispense IP	X	X	X	X	X	X
Up-titration ^j			X	X	X	
Collect blood for						
Haematology panel (predose as applicable)	X		X	X	X	X
Serum chemistry (including eGFR calculation; predose as applicable)	X		X	X	X	X

Table 10 Treatment Period Study Procedures

Visit Number	V4 ^a	V5	V6	V7	V8	V9 ^a
Procedure / Study Day	D1	D2, D3, D4	D5	D12	D19	D32
Lipase and amylase	X		X	X	X	X
Calcitonin	X					X
Lactate	X					X
Fasting lipid profile	X					X
Fasting glucose	X					X
HbA1c	X					X
PK for MEDI0382 ^k	X		X	X	X	X
Samples for potential future metformin PK analysis (predose) ^l	X		X	X	X	X
ADA ^m	X			X		X
[REDACTED]	■					
[REDACTED]	■					■
MMTT (collect samples for glucose only at all time points) ^o						X
Collect urine for						
Pregnancy test (women of childbearing potential only) ^p					X	
Urinalysis (dipstick; predose as applicable)	X		X	X	X	X
Urine albumin/creatinine ratio ^q	X		X	X	X	X

- Day 1 predose and Day 32; postural blood pressure supine and then standing should be performed
- Days 5, 12, 19, 32; vital signs to be taken prior to fitting ABPM device
- e Subjects will be fitted with the ABPM device while at the clinical unit, which may involve practice inflations. The ABPM device should be applied on the opposite arm to the arm where the CGM device is applied. The subject will then wear the monitor/cuff for approximately 24 hours and will remove at the end of the 24-hour period whilst at home and will return the ABPM device at their next visit.
- f A digital ECG recording should be performed predose and 2 hours post-dose after the subject has rested for 10 minutes in the supine position on Days 1 and 32. No specific time point is required for other visits.
- g Body weight should be measured in the morning prior to breakfast (predose on Day 1); refer to Section 4.3.1.3 for details.
- h [REDACTED]

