- i Dosing will occur daily from Day 1 to Day 32 inclusive. Subjects are required to be dosed at the clinic for the [REDACTED] dose and on study day visits when predose procedures are required (Days 5, 12, 19, and 32). See Section 4.3 for further information. Ideally subjects should self-administer doses under supervision and study site staff should ensure that the subject self-administers the first dose of IP delivered via PFS on Day 5 to ensure that they are confident in self-injecting via PFS at home.
- j Up-titration steps will be performed on Day 5 (dose will increase from [REDACTED]), Day 12 (dose will increase from [REDACTED]) and Day 19 (dose will increase from [REDACTED])
- k PK Sampling Schedule for MEDI0382:
 - Day 1: Predose
 - Day 5: Predose
 - Day 12: Predose
 - Day 19: Predose
 - Day 32: Predose and at 0.5, 1, and 2 hours (\pm 15 min); 4, 6 and 8, (\pm 30 min) postdose
 - Day 33: 24 hours (\pm 15 min) postdose
- l Samples will be collected for potential future metformin PK analysis only in subjects who are taking metformin (metformin PK samples are to be taken prior to metformin dose administration and therefore subjects should be advised to delay their morning metformin dose until after this blood test on these study visits.)
- m ADA sampling schedule: Day 1 predose; Day 12 predose; Day 32 predose
- n During the informed consent process subjects will be asked to provide consent for the main study [REDACTED] Only sample(s) for which the subject has consented will be taken.

- o MMTT schedule: Following a minimum 8-hour fast overnight and where relevant, 2.5 hours after taking the IP, a blood sample for glucose will be taken immediately prior (within 15 minutes) to the subject drinking one entire can of Ensure Plus as a standardised meal (ie, “0 minutes”). Blood samples for glucose will additionally be drawn at 15, 30, 45, 60, 90, 120, 180, and 240 minutes (± 5 min) after consumption of the standardised meal. [REDACTED]
- p A urine pregnancy test should be conducted on any female subject of childbearing potential as detailed in the schedule. Pregnancy tests do not need to be conducted in women who are surgically sterile (ie, bilateral tubal ligation, bilateral oophorectomy, or complete hysterectomy) or are postmenopausal (defined as at least 1 year since last menses and/or having an elevated follicle stimulating hormone laboratory value which is in the postmenopausal range in previous laboratory test results).

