2.2 Study Design

This is a randomized, double-blind, placebo-controlled study to evaluate the safety, tolerability, efficacy, and PK profile of MEDI0382 titrated from [REDACTED]

administered once daily by subcutaneous (SC) injection for 32 days in subjects with T2DM and renal impairment ($30 \leq \text{eGFR} < 60 \text{ mL/min/1.73 m}^2$). The study has a 14-day run-in period of diet and exercise and continuous glucose monitoring (CGM), a 32-day treatment period and a 28-day follow-up. Forty (40) subjects across multiple study sites will be randomized in two strata (Insulin dose ≥ 20 U/day or Insulin dose < 20 U/day) [REDACTED]. In addition, at least 40% of randomized subjects will have screening eGFR values between 30 and 44 mL/min/1.73 m², inclusive and at least 40% of randomized subjects will have screening eGFR values between 45 and 59 mL/min/1.73 m², inclusive although there is no stratification based on screening eGFR to ensure balance within insulin strata or treatment groups.

Mixed-meal tolerance tests (MMTT) will be performed on Day -5 and Day 32. Subjects will wear a continuous glucose monitoring (CGM) sensor from the start of the run-in period until the first post-treatment follow-up visit. 24-hour ambulatory blood pressure monitoring (ABPM) will be performed 5 times during the study (pre-treatment and 4 during treatment evaluations). Vital signs, ECG, weight, [REDACTED] measurements will be collected during the study.

An interim analysis will be performed using data collected within 12 weeks after the first subject's first dose or after 20 subjects have completed 32 days of dosing, whichever occurs sooner. This interim analysis will be performed to plan Phase 3 studies and will not be used to modify the conduct of this study.

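### The secondary 24-hour pulse-rate and blood-pressure endpoint is set at Days 4, 11, 18 and 32, but the monitor is scheduled on Days 5, 12, 19 and 32, and its planned ANCOVA appears only in the synopsis

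*Protocol*

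**What the plan says.** **Endpoint.** Protocol 2.2, Table 2, lists among the secondary safety endpoints the change in mean 24-hour pulse rate and systolic and diastolic blood pressure "from baseline (Day -5) to the end of dosing at each dose level (Days 4, 11, 18, and 32"). The synopsis has the same definition: "from baseline (Day -5) to the end of dosing at each dose level (Days 4, 11, 18 and 32").

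**Dosing blocks.** The synopsis describes active treatment as "once daily for 4 days, followed by [REDACTED] daily for 7 days, [REDACTED] daily for 7 days, and [REDACTED] daily for 14 days".

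**Recordings.** Table 10 (Protocol 4.2.2) marks ABPM at Visits 6, 7, 8 and 9 and leaves Visits 4 and 5 blank. Its footnotes confirm the days: "Days 5, 12, 19, 32; vital signs to be taken prior to fitting ABPM device". The device is fitted at the clinical unit, and "The subject will then wear the monitor/cuff for approximately 24 hours"; it comes off at home. Clinic dosing is required "on study day visits when predose procedures are required (Days 5, 12, 19, and 32"). Another footnote says "Up-titration steps will be performed on Day 5" and goes on to name Days 12 and 19. SAP 2.2 says that ABPM "will be performed 5 times during the study (pre-treatment and 4 during treatment evaluations").

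**Analysis.** The synopsis plans an ANCOVA for the 24-hour means, with treatment and the baseline measurement in the model. Protocol 4.8.6.1 says only that the change will be summarised at each post-baseline evaluation. SAP 3.5.5.2 gives descriptive summaries of the 24-hour means by insulin stratum, treatment and visit.

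**The concern.** The endpoint asks what pulse rate and blood pressure look like once a subject has completed each dose level. The schedule records them on the day the subject moves to the next level. If results from Days 5, 12 and 19 are reported under the endpoint's end-of-level wording, an effect seen on the first day of one level is credited to the level before it. In a titration study with pulse rate and blood pressure as named safety measures, that attributes the effect to the wrong dose step.

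The second part concerns the comparison itself. A programmer working from the SAP would produce descriptive tables of means. The between-arm, baseline-adjusted estimate planned in the synopsis might never be produced, or its form might be settled after the data are seen.

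**Working it through.** **1. Reproduce the endpoint days.** The blocks are 4, 7, 7 and 14 days from Day 1, so the cumulative sums are 4, 4+7 = 11, 11+7 = 18 and 18+14 = 32. The levels occupy Days 1–4, 5–11, 12–18 and 19–32. The stated endpoint days are exactly the last days of the four levels, so they look deliberate rather than mistyped.

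**2. Place the scheduled recordings on the same calendar.**

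| ABPM fitted | Level dosed from that day | Position in level | Endpoint day? |
|---|---|---|---|
| Day 5 | 2 | day 1 of 7 | no |
| Day 12 | 3 | day 1 of 7 | no |
| Day 19 | 4 | day 1 of 14 | no |
| Day 32 | 4 | day 14 of 14 | yes |

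One of four days matches, and three of four (75%) do not. Level 1 has no recording fitted on any of its dosing days, and level 4 has two. Day 4 falls within Visit 5, which has no ABPM. Days 11 and 18 have no visit at all.

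**3. Check for unlisted recordings.** Day -5 plus Days 5, 12, 19 and 32 makes 1 + 4 = 5 recordings. SAP 2.2 also counts five, one before treatment and four during it. Nothing is left over for Days 4, 11 or 18.

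**4. Is this only a one-day label shift?** If the cuff is fitted h hours before the stepped-up dose and worn for 24 hours, the share of the recording after that dose is (24 − h)/24. The documents do not state the order of fitting and dosing, so h is an assumption:

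- h = 0, or fitted after dosing: 24/24 = 100%
- h = 2: 22/24 = 91.7%
- h = 4: 20/24 = 83.3%

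Across this range the recording mainly measures the new level. A predose blood sample at the same visit does look back at the previous level; a recording worn forward does not.

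**5. Set the analysis passages side by side.**

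| Place | Quantity | Method |
|---|---|---|
| Synopsis, statistical analyses | 24-hour means | ANCOVA with treatment and baseline |
| Protocol 4.8.6.1 | change in 24-hour averages | summarised; no model named |
| SAP 3.5.5.2 | 24-hour means; change not mentioned | descriptive |
| SAP 3.5.5.1 (vital signs, for contrast) | values and change from baseline | descriptive |

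The general ANCOVA statements in Protocol 4.8.3.2 and SAP 3.4.2.3 cover secondary efficacy endpoints. Table 2 classes this endpoint as safety, so they do not fill the gap.

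**The case against.** The best reply is that the operational schedule is unambiguous and every analysis passage is keyed to recordings actually taken, by time point, post-baseline evaluation or visit. Usable output will therefore exist, and harm arises only if someone reports it under the Table 2 labels. This is fair and limits the weight of the point. It does not repair the endpoint, because a result at Day 5, 12 or 19 is a different quantity from the one defined.

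Parts of the documents are also out of sight. The dose-escalation section and the safety-endpoint rationale are redacted, and the German local amendment named in the SAP is not supplied. An explanation of the timing could lie there. However, the ABPM days, visits and wear time are all visible, and a rationale cannot add recordings that Table 10 and the SAP's count leave out. Protocol 4.3.6.2 says subjects are trained to set up and apply the device, which bears on whether home recordings would be feasible, but no home recording is scheduled for Day 11 or 18.

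On the analysis, the synopsis is part of the protocol, so the ANCOVA is prespecified, and a promise to summarise does not exclude a model. Table specifications also sit in a programming plan that is not among the documents. What remains is that the SAP, where the protocol places the detail, names neither the model nor change from baseline. That is closer to an omission than to a direct conflict, and it is the lesser half of the point.

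**Conclusion.** The concern holds. As defined, the endpoint has a scheduled recording at one of its four on-treatment time points. At the other three, the nearest recording starts on the first day of the next dose level. This follows from the stated block lengths and the assessment table alone and does not depend on when the cuff is fitted relative to the dose; only the 83.3% to 100% range does.

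The analysis of the endpoint is also unsettled: an ANCOVA in the synopsis, no model in Protocol 4.8.6.1 or SAP 3.5.5.2, and no change from baseline in the latter. This should be fixed, but it is confined to a secondary safety endpoint. The primary endpoint, sample size and power do not depend on it.

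**What to change.** **Endpoint days.** Reconcile the synopsis and Protocol 2.2 with Table 10. If the schedule stands, restate the endpoint at Days 5, 12, 19 and 32. Describe the first three as the 24 hours starting at each up-titration visit and only Day 32 as the end of a dose level, and carry the same labels into the SAP 3.5.5.2 outputs. If end-of-level values are what is wanted, the assessment schedule would have to change instead: Day 4 is already a clinic visit, but Days 11 and 18 are not. Which passage yields is for the sponsor to decide.

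**Analysis.** Bring Protocol 4.8.6.1 and SAP 3.5.5.2 into line with the synopsis. Specify an ANCOVA on change from Day -5 with treatment and the baseline value, and report the adjusted difference and its confidence interval at each time point. Modelling the value or the change gives the same treatment estimate once baseline is in the model. Adding the insulin stratum is optional and is not part of the protocol's stated model.

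**Cost.** Wording in the synopsis, Protocol 2.2, Protocol 4.8.6.1 and SAP 3.5.5.2, plus 3 measures × 4 time points = 12 model estimates, with no multiplicity adjustment, as SAP 3.1 already states. If the schedule is kept, the trial concedes that it has no end-of-level ABPM for the lower dose steps.
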